During the approximately 2-hour Visit 1, the prospective subject will be given an oral exam by one of the team dentists to insure that the dentition, periodontium, temporomandibular joints, muscles of mastication are sufficiently healthy and stable for the safe participation in the study. If determined to be sufficient, the subject will then be fully enrolled in the study and have the study and tasks explained in greater detail. Dental impressions will then be obtained as models for the fabrication of the custom oral appliances.

k. Potential risk to subjects

The minor physical risk associated with the sleep-monitoring aspects of this study are no more than those involved with standards test of bodily (physiological) functions, for example wearing a heart monitor. The oral appliances are FDA cleared and are in wide use by dental patients throughout the US. The oral appliances (OAs) are FDA cleared and are in wide use by dental patients throughout the US. The OAs may cause pain in the jaw joint and teeth, and difficulty in opening or closing the jaw; these conditions are usually temporary. In the long term, the OAs may cause changes in tooth position and in the bite (occlusion), as well as damage to the teeth and gums. What makes this experience "research" rather than "routine clinical care" is that (1) the participants are randomly assigned to one OA or the other during the two active phases of the study, and (2) additional physiological measurements will be made beyond what are typically gathered during standard clinical practice. All of these tests are noninvasive.

We do not anticipate any significant physical risk from participating in this study. Though unlikely, some subjects may experience itching or rashes from the adhesive hypoallergenic electrodes of the Medibyte or the SleepImage devices. The pulse oximeter may cause some minor irritation of the finger or finger nail. By wearing an OA, a subject may experience some discomfort and/or reduced function of the jaw joint (temporomandibular joint) and muscles of the jaw (masticatory muscles) and of the face during and after treatment. Subjects may also experience some reduction in sleep quality due to discomfort while getting used to wearing the OA (acclimation). Other minor risks include temporary irritation of the mouth and oral cavity due to contact with the OA, and excessive salivation or dry mouth from mouth breathing. Repositioning of the lower jaw and tooth movement may also occur, but are typically minor and reversible. Also highly unlikely, a subject could swallow or aspirate part of an OA should it break.

I. Potential benefits to subjects

- Two customized oral appliances to keep upon completion of the study at no cost to the subject (value of \$4600)
- 2. Effective devices that do not require electricity to operate, so can be used anywhere
- 3. Reduced apnea and snoring
- 4. Improved sleep quality and continuity

- 5. An effective treatment for obstructive sleep apnea that does not require wearing a face mask
- 6. No air pressure blowing through nose
- 7. Receiving information on sleep quality.
- 8. The researchers or study coordinator will discuss possible options that might be of benefit if a sleep issue is discovered.

Study Limitations

Hyperarousal response to the OA. Possible brief OA acclimation (4-weeks) and washout (1-week) period. No placebo device as a control condition. Interrater variability of HST polygraphy scoring. No controlled sleep environment which allows for variability in external conditions during sleep recordings. Absence of conventional sleep staging based on EEG activity.

- Adverse events and adverse device effects
 - 1. Definitions
 - i. Adverse Event (AE)

Any untoward medical occurrence, unintended disease or injury or any untoward clinical signs (including an abnormal laboratory finding) in subjects, users or other persons whether or not related to the investigational OAs. This includes events related to the investigational devices and this includes events related to the procedures involved (any procedures in the clinical investigation plan). For users or other persons this is restricted to events related to the investigational OAs.

ii. Adverse Device Effect (ADE)

Adverse event related to the use of the OA. This includes any adverse event resulting from insufficiencies or inadequacies in the manufacturer's instructions for use, the deployment, the installation (customization procedure), or any malfunction of the investigational devices. This includes any event that is a result of a use error or intentional misuse.

iii. Serious Adverse Event (SAE)

A serious adverse event is considered when it:

- a. Leads to death.
- b. Leads to a serious deterioration in health that either resulted in a life-threatening illness or injury, or resulted in a permanent impairment of a body structure or a body function, or required in-patient hospitalization or prolongation of existing hospitalization, or resulted in medical or surgical intervention to prevent life-threatening illness or injury or permanent impairment to a body structure or a body function.

This includes device deficiencies that might have led to a serious adverse event if a) suitable action had not been taken or b) intervention had not been made or c) if circumstances had been less fortunate. These are handled under the SAE reporting system.

A planned hospitalization for pre-existing condition, or a procedure required by the Clinical Investigation Plan, without a serious deterioration in health, is not considered to be a serious adverse event.

iv. Unanticipated Serious Adverse Device Effect

Unforeseeable serious adverse device events, are those having severity and occurrence not identified in the latest version of the report of the risk analysis. Consideration will be given to the:

- severity of the event
- corrective measures
- preventions from re-occurrence

The corrective measures are to be determined immediately and to be implemented. It is to be assessed whether the study can be continued.

The investigator(s) must determine whether the complication which may occur, was expected or unexpected. For this he or she must review the personal conditions and medical history of each study subject in question and determined, if the event was referenced in the protocol. An unexpected event is an event, which has not been mentioned in the study protocol.

v. Documentation and reporting of SAEs

Every adverse event that meets the criteria for an unanticipated problem must be reported to the IRB within 5 days.

vi. Protocol deviations

The Principal Investigator(s) is responsible for the conduct of the clinical trial. The PI will follow established procedures for the evaluation, approval and implementation of deviations to the study protocol and the reporting of protocol deviations as appropriate to the IRB.

vii. Early study termination

The study will be suspended immediately if unexpected high levels of complications occur and /or Adverse Device Effects occur which are unexpected in nature and/or severity as determined by the investigator(s) or IRB. The trial will not be resumed without IRB approval.

viii. Quality control

Study monitoring procedures ensure that the clinical trial is conducted in accordance with the study's protocol, standard operating procedures (SOPs), Good Clinical Practice (GCP), and applicable requirements. Trained and qualified members of the trial team will conduct investigational site visits throughout the study period in coordination with the Study Coordinator.

ix. OAs and sleep recording devices accountability

The physical location of all devices from shipment of devices to the clinical investigation site until return or removed from use due to malfunction will be documented by the Study Coordinator or Principle Investigator. The clinical investigation site also maintains controlled access to the investigational and recording devices and maintains that devices will only be used according to the study protocol. The investigation site must maintain records documenting the receipt, use, return and malfunction of the investigational device and sleep recorders with date of receipt, identification of device with serial or ID number, dates of use, subject identification, date on which investigational device was returned from subject, and date of unused or malfunctioning devices.

VIII.Ethical Considerations

The rights, safety, and well-being of the study's subjects are the most important considerations and will prevail over the interests of science and society. The available non-clinical and clinical information associated with the investigational OAs is adequate to support the proposed clinical trial. The clinical trial is scientifically sound and has been described in a clear, detailed protocol herein.

The trial will be conducted in compliance with the protocol that has received prior Institutional Review Board (IRB) approval.

The care given to and decisions made on behalf of, subjects will be the responsibility of a qualified dentist and each individual involved in conducting the trial will be qualified by education, training, and experience to perform his or her respective task(s).

Freely given informed consent will be obtained from every subject prior to clinical trial participation. All clinical trial information will be recorded, handled and stored in a way that allows its accurate reporting interpretation and verification.

The confidentiality of records that could identify subjects will be protected, respecting the privacy and confidentiality rules in accordance with the applicable regulatory requirements.

IX.Schedule

The study duration will be approximately nine months. Each subject from the time of initial OA use and sleep data recording will be involved in the study for approximately 9 weeks. (Figure 6)

a. Recruitment criteria & methods: Potential study participants will be recruited from the Texas A&M College of Dentistry (TAMCD), local A.W.A.K.E. group. Invitation to participate in the study will be by bulk email and posted flyers. The study will be registered with ClinicalTrials.gov. Data analyst and subjects will be blinded to treatment device type (i.e. sequence of use of the two OAs) and subject's identity will be coded.

b. After meeting the study's inclusion and exclusion criteria through telephone screening, study subjects will receive detailed information about the study from the Study Coordinator during their first appointment. The first appointment to the study center will include obtaining a copy of the patient's PSG/CPAP study reports and medical history, completion of the study's intake assessment, signing the informed consent form and obtaining impressions and protrusive bite. In the absence of a current PSG, subjects will be sent home with a HST to collect comparable baseline information. Both oral appliances will be constructed prior to the second appointment. The subjects will be randomized to an OA device at second appointment (this will allow any questions by the lab of the dentist to improve the device). During the second appointment, subjects will be examined and fitted by the dentist with both OAs. Subjects will be then scheduled within 4-weeks for the first HST with simultaneous SI recording for determination of the RDI and sleep quality criteria. Recordings will occur x1/subject at T₁ (first night in week-1 with first OA), T₂ (after four weeks using first OA), a washout period of 1 week using a mandible repositioner daily and CPAP nightly, T₃ (first night of week-6 with second OA) and T₄ (after four weeks using second OA). (Figure 1, below; Table 1)

c. Table 5: Protocol for determining subject candidacy:

EVALUATION	PURPOSE	PROCEDURE/RATIONALE
Recruitment / Orientation	Provide information about the study.	Provide the subject with information regarding the OA devices, the clinical study and an information brochure.
Medical Background Information	Gather information regarding the subject's medical background to determine candidacy, and recent sleep study evaluations.	Standard medical case history and physical with emphasis on OSA to include the Medical/Surgical History as part of the Case Report. Conducted individually by the team/Study Coordinator and discussed collectively to ensure that the subject has realistic expectations for the study.
Craniofacial & Oral Testing	Verify subject qualification with a craniofacial / oral exam.	Clinical assessment is performed to examine the upper airway and oropharynx to determine the subject qualification for using OA therapy.
Informed Consent	Obtain informed consent.	Informed consent will be obtained by providing information related to the time commitments of the trial, risks and contraindications.

d. Table 6: Protocol For Pre-OA Evaluations

EVALUATION	PURPOSE	PROCEDURE/RATIONALE
Pre-study AHI	Subject's own baseline AHI data for comparison to OA response	PSG or PG conducted within up to 1 year before study inclusion for baseline AHI/RDI
Pre-study questionnaire	Quality of life questionnaire for comparison to OA response	Complete the Epworth sleepiness scale and quality of life or functional outcomes sleep questionnaire. This data will be performed on the same day as sleep studies $(T_{1\text{-}4})$.
Snore Index	Baseline snore index for comparison to OA response	Data collected as a part of PSG.
Number of Periodic Limb Movements (PLMS)	Baseline number of PLMS with arousals to determine study inclusion or exclusion	Data collected as a part of PSG. This is a study exclusion criteria.
Number of Central Sleep Apnea (CSA) events	Baseline number of CSA events to determine study inclusion or exclusion	Data collected as a part of PSG. This is a study exclusion criteria.

Table 4: Protocol for OA use and home sleep recordings

TASK	PURPOSE	PROCEDURE/RATIONALE
Oral Appliance, Home Sleep Test and	To instruct subjects on how to apply, use, care for, remove	Explain and demonstrate OA use; provide instructions regarding the correct application and
SleepImage recorders orientation	and return the OAs, sleep recorders to obtain optimal recordings.	removal of HST electrodes and sensors. To provide instructions on care and return of study equipment for optimal data collection and timely return of equipment.

Completion of sleep diary and questionnaires	To instruct participants on how and when to complete the sleep diary and questionnaires.	The proper completion of the sleep diary and questionnaires facilitates assessment of the study's secondary outcome measures.
Adverse Device Effects reporting	To instruct the study subject on the definition of an Adverse Event and how to report an event.	To ensure the study subject's safety and health, whether or not the changes are believed to be device related.

References

- 1. Punjabi N. (2008) The Epidemiology of Adult Obstructive Sleep Apnea. Proc Am Thorac Soc. 5(2): 136-143.

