OSA begins with sleep onset, is commonly due to collapse of the UA and almost all patients with OSA snore.²⁴ At sleep onset, the UA undergoes both functional and structural changes, leading to spatially and temporally distributed sites conducive to snore sound generation.²² Particularly in a supine sleep position, reduced genioglossus muscle tone allows the tongue to fall posteriorly towards the pharyngeal wall. Encroachment of the tongue into the airflow lumen increases airflow turbulence, thus producing soft tissue vibration and snoring sounds. Other factors also impact the airway's luminal diameter including obesity, craniofacial abnormalities like micrognathia and retrognathia, enlarged palatine tonsils and uvula, a high-arched palate, nasal septal deviation, large tongue, long soft palate and small airway lumen. Nasal valve collapse Gender differences, age and genetic factors may also have an impact on airway resistance. Sedatives can further relax the airway's musculature and alcohol's sedative effect increases snoring and apneic events. Cigarette smoking can cause inflammation within the oral cavity reducing the lumen's size. ²⁵

Partial closure of the airway during sleep that results in reduced airflow from 30-50% for ≥ 10 seconds with maintained respiratory effort and associated oxygen desaturations is defined as an obstructive hypopnea. Cessation of airflow for ≥ 10 seconds with maintained respiratory effort and associated oxygen desaturations of 2-4% is defined as an obstructive apnea. Both events are followed with an autonomic arousal, increase in muscle tone and resumption of breathing effort. It is the cumulative number of apneas and hypopneas divided by the number of hours of sleep that results in the AHI. 3

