An increase in oropharyngeal space created by advancement of the mandible occurs in association with inferior movement of the condyles that causes the posterior aspect of the mandible to move away from the maxilla (Christensen's phenomenon). ²¹ The mandible's forward movement away from the maxilla stretches and tightens the lateral walls of the pharynx with the superior constrictor muscle through attachments that includes the tongue. ²¹ Furthermore, this space creating forward movement allows the tongue to rest behind the upper incisors to form an air seal with the soft and hard palate that then facilitates nose breathing. ²¹ An OA's mechanics to move the mandible forward should increase oropharyngeal space with concomitant reduction in the number of apnea and hypopnea events through increased forward torque on the lumen's surrounding musculature.

Midline Traction OA	Bilateral Thrust OA

Provides customized fit for each patient	√	√
Uses separate upper and lower tray pieces	V	√
Advances mandible incrementally	√	√
Advancements performed by a dental sleep specialist	√	√
Single contact point between upper and lower trays	V	
Pulls mandible forward	√	
Two contact points between upper and lower trays		√
Pushes mandible forward		√

V.Hypothesis

 $\rm H_0$: The RDI will not differ when treating adults with moderate to severe (>15 events/hour) OSA between the MT and BT devices. $\rm H_A$: The MT device / intervention will provide greater reduction in the RDI from pretreatment values than the BT device in adults with moderate to severe OSA. Secondarily, proportions of responders to MT device intervention who's RDI is reduced to an acceptable level (< 10 events/hour or >50% change from pre-treatment values) is expected to be higher with MT therapy.

VI.Objectives

The main study objectives are to:

- 1. Quantify the RDI with each OA at the start and end of four weeks of use.
- 2. Compare the RDI of each OA with pre-treatment PSG determined AHI to evaluate the percent reduction.
- 3. Characterize global sleep quality changes associated with the use of the OAs.

We endeavor to model real-world conditions for measuring sleep by utilizing HST and recording in the subject's own sleep environment. Based on previous research, we expect reduction in the RDI with OA use and superior response with the MT OA.

VII.Methods

- a. Study type
 - 1. Single center, cross-over randomized control trial; superiority trial

2. Interventional comparative effectiveness research

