b. Population

- 1. Adults (n=44) with moderate to severe OSA.
- 2. Potential study participants will be recruited by means of flyers posted at the College of Dentistry, Dallas A.W.A.K.E. office (support group for sleep apnea patients) and Dallas area sleep clinics. Online postings at clinicaltrials.gov and the College web site. Also post flyers at (1) regional hospitals and clinics, (2) city and county offices/stations (such as the Dallas Fire Department), (3) DART and other transportation offices and (4) Facebook, Twitter and similar site, (5) local newspapers and magazines, (6) local radio stations. The content of the advertisements on venues (5) and (6) will be the same as the approved flyers. Written permission will be sought from all sites at which flyers are to be posted. Data analyst and subjects will be blinded to treatment device type (i. e. sequence of use of the two OAs) and subject's identity will be coded.
- 3. Controls and Controlling Confounders: Subjects serve as their own controls; their baseline polysomnography (PSG) or Home Sleep Test (HST), untreated values (from full or split night PSGs) will serve as their control values for evaluating treatment effects with each of the two OAs. The focus of the trial is on comparing OA appliance efficacy in reducing the RDI (AHI); the presentation, fitting, monitoring and adjustment of the two OAs will be the same for both arms of the study. For the operators, there will be concealed allocation of assignment of subjects to treatment.
- 4. Performance Site: Texas A&M College of Dentistry, [name]. Seventh floor room 725, two operatory clinic.

c. Inclusion criteria

OSA diagnosed adults, at least 18 years old, who have been recently diagnosed by polysomnography (PSG) or polygraphy home sleep test (HST) in the previous year and are currently being treated with continuous positive airway pressure (CPAP) having an AHI > 15 events/hour of sleep; two or more OSA symptoms (snoring, witnessed apnea or daytime hypersomnolence complaint); at least 8 teeth per arch to support either OA device; Mallampati score from I to III; Palatine tonsils – grade 0, 1, or 2; Central and mixed apnea index < 5 events /hour. Consent to study's timeline; willingness to wear home sleep test apparatus for at least 4 nights and to wear an oral appliance every night for 8 weeks; willingness to pick up and return home sleep test kits as needed.

d. Exclusion criteria

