Cardiac & pulmonary disease (e.g., congestive heart failure, severe arrhythmias, COPD); central sleep apnea; comorbidities of other sleep disorders other than OSA; no active TMD or jaw muscle pain, morphological airway abnormalities, BMI ≥35; pre-existing difficulty swallowing; throat or neck related health issues; endocrine dysfunction; severe psychiatric disorders; intellectually disabled; previous OA therapy; previous ENT surgery; restrictions in jaw opening; pregnant / breast feeding or intent to become pregnant during the study; inability to provide informed consent and apply the HST recorders.

e. Table 4: Variables of Interest: Primary, Secondary and Exploratory

Prima	ry	Secondary	Exploratory
with f of-tre secon treatn OA; T	art-of-treatment irst OA; T ₂ -end-atment with d OA; T ₃ -start-of-nent with first f ₄ -end-of-nent with second	T ₁₋₄ Snore count; OA compliance; Mean disease alleviation; Sleep Quality T _{0, 2, 4} Epworth Sleepiness Scale score; Short Form-36 score Thornton snoring scale Sleep observer scale Symptom alleviation Changes in occlusion as measured by shim stock, tested before and after	T ₄ OA device preference and perceptions of comfort; Development of a cost effective titration protocol with maximal patient convenience.

Mean disease alleviation is a composite measure of the reduction in RDI and OA compliance. RDI, respiratory disturbance index equals the number of respiratory events per hour of recorded time; $T_{1,4}$, time points 1-4

- f. Data collection techniques to be used during sleep
 - 1. OA compliance
 - i. This variable is determined by the number of hours that the OA device is worn per hour of sleep per night using Braebon monitors (integrated chips; Kanata, Ontario, Canada)
 - 2. Respiratory measures (Figure 3)
 - Braebon polygraphy (PG) recorder for home sleep testing: airflow, respiratory effort, electrocardiogram (ECG), pulse oximetry, anterior tibialis electromyography, body position, and snore sound.

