The PG unit is a category Type III sleep testing device. Manually scored sleep disordered breathing events will be categorized as apnea or hypopnea (RDI; ≥ 5 , >15, >30 events/hour) and phenotyped as either obstructive or central type events. Mixed events will be assigned to the OSA category. The definition of apnea to be used will be a $\geq 90\%$ reduction in airflow from baseline and ≥ 10 seconds in duration. Hypopnea will be defined as a reduction in airflow of $\geq 30\%$ with an associated oxygen desaturation. The RDI will be defined as the number of apnea-hypopnea events divided by recorded hour. $^{3, 24}$

- 3. Sleep quality assessment (Figure 4, 5)
 - SleepImage (MyCardio, LLC, Broomfield, CO) recorder: ECG, actigraphy, body position, snore, ECGderived respiration

The SleepImage system includes a sleep recorder that is clinically validated and FDA cleared to allow the non-intrusive collection of objective measures of sleep quality. The ECG-recorder with cardiopulmonary coupling (CPC) analysis collects ECG, actigraphy, snoring and body position data at a sampling rate of 600 Hz that is later filtered to sampling rates of 200, 40, 10 and 10 Hz, respectively. The ECG-recorder's sleep data are uploaded and scored automatically. CPC algorithms assess the ECG's R-wave amplitude change associated with tidal volume dynamics to derive a respiration (ECG-derived respiration) signal. The resulting sleep spectrogram, divides sleep states into "stable sleep" (0.1–0.4 Hz) and "unstable sleep" (0.01–0.1 Hz). Within 0.01-0.1 Hz is the "narrow band" that identifies central-periodic type patterns (0.006–0.1 Hz) and obstructive type events primarily through a "broadband" (0.0–0.01 Hz, not fitting narrow band criteria) pattern. ^{27, 28} Between-treatment differences in the proportions of stable and unstable sleep will be evaluated.

Subjective measures related to the sleep experience of the subjects will also be collected using these questionnaires at T_0 , T_2 and T_4 : Eppworth sleepiness scale, Quality of Life Short Form-36, version 2 and the Thornton snoring Scale.

g. Data collection

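### Objective 2 measures percent reduction from a per-sleep-hour baseline (PSG AHI) to a per-recorded-hour result (RDI), so for PSG-baseline subjects the denominator alone inflates it

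*Combined protocol and SAP*

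**What the plan says.** All references are to the combined protocol and SAP, within section 12.1.

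- **AHI (III, Theoretical framework):** "It is the cumulative number of apneas and hypopneas divided by the number of hours of sleep that results in the AHI".
- **RDI (VII.e, note to Table 4):** "RDI, respiratory disturbance index equals the number of respiratory events per hour of recorded time". VII.f.2 agrees: "The RDI will be defined as the number of apnea-hypopnea events divided by recorded hour". All T1 to T4 values are RDI.
- **Comparison (VI, Objective 2):** "Compare the RDI of each OA with pre-treatment PSG determined AHI to evaluate the percent reduction".
- **Responder rule (V, Hypothesis):** "< 10 events/hour or >50% change from pre-treatment values", with a higher proportion of responders expected on MT.
- **Baseline source (IX.d, Table 6):** "PSG or PG conducted within up to 1 year before study inclusion for baseline AHI/RDI". VII.b.3 allows full-night or split-night PSG or a home test, and treats the two indices as one: "comparing OA appliance efficacy in reducing the RDI (AHI)". IX.b sends a subject home with a home test only when there is no current PSG.
- **Secondary composite (note to Table 4):** "Mean disease alleviation is a composite measure of the reduction in RDI and OA compliance". Its baseline is not named.

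The investigative question (II.c) adds a third denominator, recorded sleep. Study Limitations lists the lack of EEG staging but not this consequence. Diaries record hours of sleep and SleepImage runs on recording nights, but neither is assigned to convert RDI.

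**The concern.** Sleep time cannot exceed recorded time. The same events therefore give an index per recorded hour no higher than the index per hour of sleep, and lower whenever the subject is awake for part of the recording. A percent reduction from PSG AHI to home RDI contains that difference as well as the device effect. Two subjects with identical response can get different percent reductions because one was diagnosed by PSG and the other by home test.

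Percent reduction is one of the three main objectives. The over-50% change is one limb of the secondary responder hypothesis, and mean disease alleviation is exposed too if it uses this baseline. One baseline serves both devices, so the distortion is not aimed at either. But BT, with the smaller expected reduction, has more subjects near 50%, so its responder rate rises more than MT's and the contrast shrinks.

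**Working it through.** The plan gives no figure for percent reduction from AHI to RDI, so there is none to reproduce. The sample size of 38 concerns the paired RDI comparison and uses no baseline.

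**Inputs from the plan.** Mean AHI reductions of 55.4% (BT) and 85% (MT), from I, Background and Significance. Table 2 supports a lower MT value. Weighting its six MT studies by patients gives (20×84 + 9×90 + 12×87 + 51×80 + 497×72 + 48×64)/637 = 46470/637 = 73%.

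**Assumed, not in the plan.** s = sleep hours / recorded hours = 0.75 to 0.90, and the same event counting on both nights.

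**Step 1, percent reduction.** With untreated index A per hour of sleep, on-device RDI = s·A·(1-r).

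- Home-test baseline s·A: reads 1 - s·A(1-r)/(s·A) = r.
- PSG baseline A: reads 1 - s(1-r), an excess of (1-s)(1-r).

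| s | reads when r = 0 | r needed to read 50%: 1 - 0.5/s | BT: 1 - 0.446s | MT: 1 - 0.15s | MT-BT: 29.6s |
|---|---|---|---|---|---|
| 0.90 | 10% | 44.4% | 59.9% | 86.5% | 26.6 |
| 0.85 | 15% | 41.2% | 62.1% | 87.3% | 25.2 |
| 0.80 | 20% | 37.5% | 64.3% | 88.0% | 23.7 |
| 0.75 | 25% | 33.3% | 66.6% | 88.8% | 22.2 |

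On matched denominators the MT-BT difference would be 85 - 55.4 = 29.6 points.

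**Step 2, who changes responder status.** On the 50% limb, only true reductions between 1 - 0.5/s and 50% change. If baseline AHI is 20 or less, any RDI below half of it is already below 10, so the mismatch cannot change the full rule.

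**Step 3, full rule by simulation.** Further assumptions: baseline AHI log-normal (median 27 before truncation, log-SD 0.35) cut at above 15; true reduction beta-distributed with SD 20 points; BT mean 55.4%, MT mean 85%; all baselines PSG. Matched means both indices are per recorded hour.

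| s | BT responders, matched → plan | MT responders, matched → plan | MT-BT gap, matched → plan | loss (points) |
|---|---|---|---|---|
| 0.90 | 63.9 → 71.0% | 92.4 → 93.9% | 28.4 → 22.9 | 5.6 |
| 0.85 | 65.2 → 75.8% | 92.7 → 94.8% | 27.4 → 19.0 | 8.4 |
| 0.80 | 66.9 → 80.7% | 93.0 → 95.8% | 26.1 → 15.1 | 11.0 |
| 0.75 | 68.9 → 85.6% | 93.4 → 96.7% | 24.5 → 11.1 | 13.3 |

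Losses were taken before rounding. Status changes for about 7 to 17% of BT subjects and 1.5 to 3.3% of MT subjects.

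**Step 4, sensitivity.**

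- MT mean 73%: loss 3.8 points at s = 0.90 and 9.7 at s = 0.75.
- Half the baselines PSG (MT 85%): loss 2.8 to 6.7.
- s = 0.80, baseline median 22/27/33/40: loss 8.4/11.0/13.1/14.2.
- s = 0.80, reduction SD 15/20/25 points: loss 15.2/11.0/8.3.

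**Step 5, does the remedy help?** Re-expressing a PSG per recorded hour, with laboratory sleep fraction sL, reads 1 - (s/sL)(1-r). This is exact if sL = s. If sL is lower, it is still nearer to r than the plan when s/sL - 1 < 1 - s, that is sL > s/(2-s): 0.82/0.74/0.67/0.60 at home s = 0.90/0.85/0.80/0.75. With home 0.90 and laboratory 0.75, a device with no effect reads 1 - 0.90/0.75 = -20%, against +10% under the plan. The simulated gap becomes 35.5 points, against 28.5 matched and 22.9 under the plan (28.4 in the Step 3 table; the 0.1 is simulation error).

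**The case against.** A reader might infer that both percent reduction and response are inflated for every PSG-baseline subject. The documents do not support that. Most subjects keep their responder status, as Step 2 shows. The formula also requires identical event counting. The home hypopnea rule gives no desaturation threshold, no rule is stated for baseline reports, and baselines may be split-night or up to a year old. Any of these could offset or add to the denominator effect in one subject; at s = 0.85, home scoring that counted 1/0.85 = 1.18 times as many events would cancel it. This limits the claim to the denominator taken alone. It does not remove it, because nothing in the plan makes those other differences cancel it.

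The size rests on inputs the plan does not give, and 85% for MT is generous against Table 2. That stands, and is why the 73% case is shown.

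The conversion can also do worse than the plan when the laboratory sleep fraction is well below home. It then errs toward MT, whose manufacturer is a named sponsor. That stands too, and the remedy must say so.

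Finally, the distortion works against the alternative hypothesis and falls on secondary analyses. That is correct, and it limits the severity.

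**Conclusion.** The concern holds in limited form. The two denominators differ, the plan does not reconcile them, and Table 6 pools both kinds of baseline. For PSG-baseline subjects the denominator alone raises percent reduction by (1-s)(1-r). At assumed s of 0.75 to 0.90, the MT-BT responder gap loses about 6 to 13 points if MT truly achieves 85%, or about 4 to 10 if 73%, with all baselines PSG; about half that if half are PSG. The net direction for an individual is not known.

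A reader might also infer that the primary result is biased or that MT is favoured. Neither follows. The primary Wilcoxon test compares RDI on MT with RDI on BT, both per recorded hour; the below-10 limb uses no baseline; and the distortion narrows the MT-BT contrast. The point should be corrected before analysis, but it does not threaten the primary comparison.

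**What to change.** 1. In Objective 2, Table 6, the over-50% limb and (if it uses this baseline) mean disease alleviation, define baseline as untreated events per recorded hour for every subject. For a PSG, divide events in the untreated portion by that portion's recorded hours; for a home test, use its own events and recorded hours.
2. Where a report lacks these figures, use the home test already planned in IX.b, and state that this night is untreated, which IX.b does not say.
3. Report the AHI-based percent reduction alongside as a sensitivity analysis, and show results and numbers by baseline type (PSG or home test).
4. State that the conversion is exact only if laboratory and home sleep fractions match, and that it can over-correct and widen the MT-BT gap if the laboratory fraction is well below home (below about 0.82 when home is 0.90, or 0.74 when home is 0.85).
5. Keep AHI above 15 as the entry criterion, and do not re-test entry on the new scale.

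The cost is wording, two figures copied from each report and, for some subjects, one more recording within the eight-night limit in section 13.6. Percent reductions will generally look smaller, and differences in event definitions between baseline and study nights will remain. An untreated study home test for all 44 subjects would remove the laboratory-home difference, but at the price of 44 untreated nights, so it is not the first choice.
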